#### 5.0 THERAPEUTIC/DIAGNOSTIC AGENTS

Rocuronium use for muscle relaxation is standard during general anesthetics at MSKCC. Sugammadex while relatively new at our institution has been used with increasing frequency for various surgical cases. Robotic prostatectomies always require neuromuscular blockade. Patients will be receiving these agents whether or not they are involved in study.

Patients routinely receive varying dosages of rocuronium. There is no consensus on "optimal" dose of rocuronium or on "optimal" depth of neuromuscular blockade; given the underlying equipoise, the dosage will be determined based on the intervention arm of the study. Patients in the deep neuromuscular blockade arm will likely receive higher aggregate dose of rocuronium. This will pose no increased risk to patient given the ability to reverse both moderate and deep blockade with sugammadex. Furthermore, the higher dosages of rocuronium and sugammadex required in this protocol do not pose increased risk to patients. Studies have demonstrated that the incidence of adverse events in the dose groups described does not indicate a dose-response relation. 

The only known drug interaction with sugammadex is Toremifene. Patients receiving Toremifene (antiestrogen family of drugs) could cause a delayed recovery from neuromuscular blockade. Patients on Toremifene will be excluded from study (see Appendix 9).

Sugammadex safety in patients under the age of 17 has not been established. All patients in this study will be 18 years or older.

Sugammadex use for patients with severe renal impairment is not recommended. Patients with severe renal impairment (defined as creatinine clearance <30 ml/min) will be excluded from this study (see Appendix 9).

#### 6.0 CRITERIA FOR SUBJECT ELIGIBILITY

#### 6.1 Subject Inclusion Criteria

- 1. Adult patients under the age of 80.
- 2. American Society of Anesthesiologists Physical Status 1, 2, 3.
- 3. Elective Robotic Prostatectomy.
- 4. Patient undergoing surgery at Josie Robertson Surgical Center

#### 6.2 Subject Exclusion Criteria

1. Age younger than 18.

- 2. Inability to provide informed consent.
- Allergy to rocuronium, sugammadex, midazolam, propofol, fentanyl, lidocaine, mannitol (IV Acetaeminophen), IV Acetaminophen, Ketorolac, Morphine, Hydropmorphone, Dexamethasone, Zofran, Bendaryl, Compazine
- Neuromuscular disease.
- 5. Any patient with previous abdominal surgery less than or equal to 20 years prior to scheduled surgery date.
- 6. Patients with BMI> 35.
- 7. Severe renal impairment (creatinine clearance <30 ml/min).
- 8. Pt receiving Toremifene or any history of receiving Toremifene.
- 9. Chronic pain patients.
- 10. Patients receiving suboxone.
- 11. Patients receiving succinylcholine.

#### 7.0 RECRUITMENT PLAN

All patients who meet all eligibility criteria and are scheduled for robotic prostatectomies performed by a surgeon listed on this protocol, will be approached to gauge interest in participating in the study.

All patients will undergo surgery at Josie Robertson Surgical Center. Potential patients will be identified by the study team ahead their scheduled preoperative visit. The study team will work closely with the urology clinic staff to ensure documents are prepared ahead of time. The consent discussion for this study will occur during the preoperative visit in the urology clinic by either the surgeon or the advanced practice provider (Nurse practitioners or physican assistants). The protocol will be described to all prospective patients by the consenting professional, who will obtain informed consent from agreeing patients. Interested patients who do not provide provide consent during their pre-operative visit will be followed up by the study team at another time prior to surgery if possible. All consent discussions will occur at least 1 day prior to the patient's surgery. There will be no compensation (financial or otherwise) to participants who enroll in the study. Accordingly, there is no direct benefit to patients who agree to participate in the study.

Surgeons involved in the study as investigators will receive a detailed fact card that will be used for their reference and to educate their patients. This fact card will include:

- 1. Background and rationale
- 2. Scientific aims
- 3. Intervention and treatment plan
- 4. Protocol summary
- 5. Contact information for PI, research study assistant

Educational program: Surgeons will receive orientation and education on all aspects of the protocol. The education sessions will first in a didactic group session one month before the start of enrollment, and followed by a one-to-one review session with the study PI one week before the start of enrollment to review details of the study.

Because of the nature of the surgical procedure, only men will be enrolled in the study. All male patients regardless of race and ethnic background will have equal opportunity to participate in the study.

To maintain uniformity in protocol execution, only the anesthesiologists and CRNAs listed as an investigator on the face sheet will be eligible to conduct the study cases.

#### 8.0 PRETREATMENT EVALUATION

There is no need for additional pretreatment evaluation and participants in the study will not receive additional testing or evaluations.

#### 9.0 TREATMENT/INTERVENTION PLAN

[figure not shown]
A total of 130 patients scheduled for robotic prostatectomies will be randomized into two groups: deep (experimental intervention group) versus moderate (control) blockade, with 120 expected to be evaluable for each of the two primary endpoints. In both groups, anesthesia will be induced and maintained per our department's current routine, and standardization will is clearly defined previously in the protocol. For each patient in either arm of the study, recovery from induction dose of rocuronium will be established before reinitiating muscle blockade (deep versus moderate) with rocuronium infusion. Level of the blockade will be monitored continuously with GE Anandic NMT device and dose of rocuronium will be titrated.

All patients will be maintained in the same surgical position (angle of Trendelenburg) per robotic urological surgery standard. All surgeons will be blinded to the 'starting IAP' value and the IAP value will be recorded at 15-minute intervals. Changes in IAP outside the 15-minute interval measurement point will also be recorded. Increases or decreases in IAP per surgeon's request will be allowed throughout the case. Surgical exposure/visualization will be assessed at 30-minute intervals using the Leiden surgical rating scale of 1 to 5. Surgeons will be alerted if IAP reaches 15, which is the standard upper limit of IAP at MSKCC. Investigators request they know the IAP at a level of 15, so they can weigh risk/benefit of continuing to operate at that higher threshold of IAP. At the end of a case, patients in both arms will be reversed with sugammadex at fascia closure. Data will be collected from the of the surgical case. Patients who experience unexpected intraoperative events including death, conversion to open procedure, a decline in clinical condition that would end a planned procedure, anaphylaxis, or a life-threatening hypersensitivity reaction to any medication will be removed from the study.

Estimated blood loss will be recorded from Electronic Medical Record. Postoperatively, endpoints (pain and nausea) will be recorded on all patients by a PACU nurse and research staff(up to 48 hours postoperatively) according to pain and nausea scales as described above. The a PACU nurse will perform these assessments while the patient is on-site. The research nurse will complete 24 and 48-hour assessments by telephone.

#### 10.0 EVALUATION DURING TREATMENT/INTERVENTION

IRB Number: 18-408 A(17) Approval date: 01-Oct-2024

#### 11.0 TOXICITIES/SIDE EFFECTS

The most common adverse reactions are vomiting, low blood pressure, pain, headache, and nausea. Sugammadex (BRIDION) may temporarily reduce efficacy of hormonal contraceptives. Severe, potentially life-threatening allergic reactions were reported in clinical trials. The incidence of severe toxicities (i.e., anaphylaxis) is estimated at 29 per million cases. In a systematic review of hypersensitivity associated with

sugammadex administration in 2014 (Sugammadex has been available for clinical use in Europe since 2008), only 15 cases met inclusion criteria. Signs and symptoms include rash (12/15 cases) and World Allergy Organization anaphylaxis (11/15 cases). Other hypersensitivity reactions that can prove life-threatening in the presence of rash are hypotension, tachycardia, or decreased SpO2 in 60%, 53%, and 47%.

There have been cases of abnormally slow heart rate (bradycardia), some of which have resulted in cardiac arrest within minutes after the administration of Sugammadex.

Surgical complications will be recorded in a uniform, recognized method using CTCAE version 5.0 to report adverse events during study followup. Type and severity of adverse events will be recorded.

In addition, per MSKCC urology standard, complications will be recorded using the Clavien-Dindo Classfication system. The therapy used to correct a specific complication is the basis of this classification in order to rank complications in an objective and reproducible manner.

#### 12.0 CRITERIA FOR THERAPEUTIC RESPONSE/OUTCOME ASSESSMENT

IAP as an endpoint and outcomes assessment (surgeon visualization, estimated blood loss, surgical operative time, postoperative pain and nausea scores) will be as follows:

#### IAP pressure:

IAP (mmHg) during pneumoperitoneum will be recorded at 15-minute intervals, and IAP will be recorded at every pressure change performed even when a change occurs within 15-minute interval.

#### IAP pressure maintenance:

After trocar insertion, the insufflation pressure will be set to the 'starting IAP'. All cases will begin at this value, which will be greater than or equal to 8 and less than 10. Surgeons will be blinded to this value. As necessary, surgeons will request an increase in pressure to improve visualization. This increase will occur at surgeon's direction and may increase and decrease per surgeon request.

### Surgeon assessment of surgical exposure/visualization:

Overall surgical conditions will be estimated by the surgeon at 30-minute intervals. The Leiden surgical rating scale will be utilized with a scale of 1-5. Where 1 is extremely poor conditions, and 5 is optimal surgical conditions. This surgical rating scale is well-established for assessing surgeon visualization in laparoscopy 

#### Estimated blood loss:

Recorded from Electronic medical record

#### Postoperative pain (primary endpoint) and postoperative shoulder pain (exploratory endpoint):

The numeric pain scale (NPS) is a subjective measure which can be used in recovery rooms to assist in the assessment of pain. Individuals rate their pain on an eleven-point numerical scale. The scale is composed of 0 (no pain at all) to 10 (worst imaginable pain).

Postoperative pain scores are assessed by PACU nurses according to the following scheme:

As per Post Anesthesia Care Unit (PACU) standard of care at Josie Robertson Surgery Center, the PACU nurses that have been trained by the PI and blinded to randomization ask the patient to rate their pain. The

actual question asked is, "on a scale from 0-10, where 0 is no pain and 10 is excruciating pain, please rate your pain." The pain assessment is administered verbally. PACU nurses ask the patient to rate their pain utilizing the NPS scale..

The trained PACU nurses will be evaluating and assessing pain per the Josie Robertson standard of care by using the Post Anesthetic Discharge Score Tool (see Appendix 8).

Hour 1 pain scores will be captured from the Nursing PACU flowsheet.

Hour 6 and 12 pain scores will be captured in the research assessment form (see Appendix 2).

Most patients on this study will be discharged before 24 hours so assessment at the 24 hour and 48-hour time points will be completed via telephone by the research staff. In the event that the patient has not been discharged from PACU at 24 and 48 hours, the pain scores will be captured in person on the research assessment form.

Postoperative shoulder pain will be defined at postoperative times of 1-hour, 6-hour, 12-hour, 24-hour and 48-hour on the research assessment form. A pain scale of 0-10 will be utilized (0 = no pain, 10 = worst pain imaginable).

Additionally, the total dose of analgesics will be recorded during the intraoperative and the postoperative periods until patient discharge.

Chronic pain patients will be excluded from the protocol.

#### Postoperative nausea:

As per the standard of care at the Josie Robertson Surgery Center, the PACU nurses that have been trained by the PI and blinded to randomization will ask the patient to rate their nausea. The actual question asked is, "on a scale of 0-10, where 0 is no nausea and 10 is the worst nausea imaginable, please rate your nausea." The nausea will be administered verbally.

The PACU nurses will record postoperative nausea and vomiting (PONV) in PACU (one-hour post-extubation) and at postoperative times of 1-hour, 6-hour and 12-hour, on the research assessment form. The 24 and 48-hour time points will be completed by the research staff on the research assessment form via telephone if the patient has been discharged before these time points are assessed.

The Apfel 4 point scale for predicting postoperative nausea and vomiting will be used. This scale includes four predictors: female gender, history of motion sickness, nonsmoking, and use postoperative opioids. As all patients in the protocol for robotic prostatectomy will be male, Apfel score will not exceed 3 in any patient. If patient received EMEND preoperatively, the patient will be included in study but the nausea data will be excluded. PONV will be assessed with a scale of 0-10 (0=no nausea and 10 worst nausea imaginable)

In addition, the total dose of rescue antiemetics in the postoperative period will be recorded.RASS scores will be assessed and collected verbally by the PACU nurse (Hours 1, 6 and 12 post-operatively); Hour 24 will be collected by phone call. This data will be captured on the research assessment form.

#### 13.0 CRITERIA FOR REMOVAL FROM STUDY

Criteria for removal of subject from the study will include patient death, surgical conversion from robotic to open procedure, intraoperative deterioration in clinical condition that would end a planned procedure.

Patients are considered evaluable for the first primary endpoint (IAP) if they can provide at least one IAP recording; patients are considered evaluable for the second primary endpoint (Pain) if they can provide at least one NPS pain score within 6-hours after surgery. Study data will be analyzed according to a modified intention-to-treat principle ("modified" because patients considered inevaluable for a given primary endpoint will be excluded from the analysis of that endpoint).

The following are a list of possible perioperative scenarios. We expect these to occur extremely infrequently. We anticipate fewer than 10 occurrences during the study period and have planned the protocol accordingly.

- 1) Cancelled surgery
  - Patient will not provide either primary endpoint therefore patients in this category will be excluded from primary analysis
- 2) Patient death
  - For patients who die in the perioperative period, any data up until patient death will be analyzed. These patients may possibly contribute data for only one of the two primary endpoints (IAP)
- Surgical conversion from robotic to open procedure
   Any data up until conversion will be analyzed.

   These patients may possibly contribute data for only one of the two primary endpoints (IAP)
- 4) Intraoperative deterioration in clinical condition that would end planned procedure For patients who experience deterioration in clinical condition that ends planned procedure, any data up until deterioration will be analyzed.
  - However, there will be an investigation to assess the possible (but extraordinarily unlikely) influence of protocol in leading to deterioration.
- 5) Deviation from protocol by giving additional dose of NMB to satisfy surgeon request for better visualization
  - All data in this scenario will be analyzed.. Secondary analysis will be conducted as treated.
- 6) Equipment failure of the neuromuscular train of four monitoring device
  Any data up until failure of neuromuscular train of four monitoring device will be analyzed.patient will
  be considered evaluable for only one of the two primary endpoints (IAP).
- Accidental unblinding of surgeon
   All data will be analyzed.. This will be an evaluable patient.
- 8) Accidental unblinding of investigator conducting postop evaluation All data will be analyzed. This will be an evaluable patient.
- 9) Accidental unblinding of patient
  All data will be analyzed. This will be an evaluable patient

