#### 14.0 BIOSTATISTICS

In this single-blinded prospective randomized study, patients will be randomized in 1:1 ratio to two arms: moderate NMB (control) or deep NMB (intervention). The two primary endpoints of interest in this study are: levels of IAP and postoperative pain. Thus, in the sample size calculation below, we consider multiple primary endpoints and power the trial to detect success in at least one endpoint. The first primary endpoint of interest is IAP. The second primary endpoint of interest is Pain scores within 6-hours post operation. To characterize the entire set of a patient's IAP measurements under insufflation, we consider the use of area under the curve (AUC). We plan to randomize 130 patients to moderate or deep NMB arms, stratified by BMI (< vs >=30) and surgeon, and expect 120 patients to be evaluable for each of the two primary endpoints. Patients are considered evaluable for the first primary endpoint (IAP) if they can provide at least one IAP recording; patients are considered evaluable for the second primary endpoint (Pain) if they can provide at least one NPS pain score within the 6-hours postoperation.

AUC is a useful clinical endpoint for the aggregate effect over time and can summarize the average response to treatment over the period of observation. AUC is an appropriate summary measure for data collected over time, and it is commonly seen in pain measurements, as well as chronic obstructive pulmonary disease (COPD), diabetes, and pharmacokinetics studies. For this study, we will use the area under the IAP curve during insufflation as a measure for the first primary endpoint which focuses on the effect of deep NMB on IAP during robotic prostactetcomy. We will consider the time-weighted measure of AUC that integrates serial

2.1

assessments of the patient's IAP measurement over time using the trapezoidal rule. The corresponding "mean AUC" (AUCmean) is obtained as AUC/duration of insufflation for each patient. From **Kim et al**, mean IAP decreased by approximately 22% (standard deviation [SD] = 1.3) from moderate NMB to deep NMB.

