Analysis of the primary endpoint which involves IAP will be AUCIAP compared between the two arms using the linear mixed-effects model: randomized arm as the fixed-effect, BMI as the adjustment covariate, with surgeon-level random effects. Transformation of the outcome may be applied if the normality-of-errors assumption is violated. As a secondary analysis, the longitudinal IAP measurements will be analyzed using linear mixed-effects models including time and randomized arm as fixed-effects with stratification variable (BMI), and patient-level random effects, nested within surgeons. In the rare case that the patient's IAP is beyond 15 the surgeon will be unblinded to the IAP, and only the IAP up to the point of unblinding will be included in the analysis. 15 is the conventional goal for the upper limit of IAP at MSKCC. Investigators request they know the IAP at a level of 15, so they can weigh risk/benefit of continuing to operate at that higher threshold of IAP. In this rare occurrence, patients will still be included in the analyses as modified intent-to-treat, including IAP values until IAP-unblinding.

Analysis of the second primary endpoint will be AUCpain within 6-hours postoperation. AUCPain analysis will be conducted with linear mixed-effect model with appropriate transformation for the outcome for normality. The model will include randomized arm as fixed-effects along with stratification variable (BMI), and patient-level random effects, nested within surgeons.

For the primary analyses, all recorded IAP will be analyzed in a modified intent-to-treat fashion. Where a patient randomized to moderate NMB crosses over to deep NMB, all recorded IAP will be analyzed under the randomized arm. As a secondary analysis of the primary outcome, we will perform an as-treated analysis where the set of IAP values will be assigned to the actual intervention received. Correlation between AUCIAP and AUCPain will be summarized using Spearman correlation coefficient. Additionally, the primary endpoints will be summarized between patients with and without neuromonitoring issues (see

Section 13.0). As a sensitivity analysis, planned analyses of both primary endpoints will be repeated after excluding patients with neuromonitoring issues (see Section 13.0).

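### A failed TOF monitor takes a patient out of the primary pain analysis (Section 13.0, item 6) even when the patient has the pain score that the general evaluability rule asks for

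*Combined protocol and SAP*

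**What the plan says.** **General rule for pain.** Section 13.0: "patients are considered evaluable for the second primary endpoint (Pain) if they can provide at least one NPS pain score within 6-hours after surgery". Section 14.0 repeats it: a patient counts "if they can provide at least one NPS pain score within the 6-hours postoperation". Neither sentence depends on TOF monitoring. Section 13.0 defines modified intention-to-treat as leaving a patient out of an endpoint's analysis only when that patient is inevaluable for that endpoint.

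**Rule for monitor failure.** Section 13.0, item 6: "Any data up until failure of neuromuscular train of four monitoring device will be analyzed", and the patient will "be considered evaluable for only one of the two primary endpoints (IAP". Section 4.1 (Intraoperative monitoring) adds that if the monitor fails, or cannot obtain a baseline, the patient comes off protocol. It does not say whether outcome collection stops.

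**Rule for IAP.** Section 14.0: "For the primary analyses, all recorded IAP will be analyzed in a modified intent-to-treat fashion". The one cut-off stated there applies when the surgeon is told the pressure because it is beyond 15: "only the IAP up to the point of unblinding will be included in the analysis".

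**Description of these patients.** Item 10 (Monitoring issues) separates its own patients, whose TOF readings are noisy, from item 6 patients, whom it describes as having no TOF readings at all. Item 10 patients stay in the intention-to-treat analyses, and in a sensitivity analysis "planned analyses of both primary endpoints will be repeated after excluding patients with neuromonitoring issues".

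**Expected frequency.** For all Section 13.0 scenarios together: "We anticipate fewer than 10 occurrences during the study period". Section 4.1 calls monitor failure unlikely and says that it was not reported in the pilot.

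**The concern.** The TOF monitor measures depth of block during surgery. Pain is scored afterwards in the PACU by nurses blinded to allocation, and the hour 1 score comes from the routine flowsheet. A monitor failure therefore does not stop a patient from giving a pain score. Such a patient is evaluable under the general rule and inevaluable under item 6.

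Two things are at stake. Following item 6 discards an observed primary outcome because of something that happened after randomisation. Following the general rule ignores item 6. The trial declares a difference if either primary endpoint reaches p≤0.025, so membership of each analysis set should not depend on which sentence the analyst follows once data are in hand.

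**Working it through.** **1. Which rule applies to whom.** The Section 13.0 scenarios, side by side:

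| Item | Event | Treatment of the data |
|---|---|---|
| 2, 3 | Death; conversion to open | Data up to the event; patient may possibly contribute IAP only |
| 4 | Deterioration ending the procedure | Data up to the event |
| 5 | Extra blocker at surgeon's request | All data kept; as-treated analysis is secondary |
| 6 | TOF monitor failure | Data up to failure; IAP only |
| 7–9 | Accidental unblinding | All data kept; evaluable |
| 10 | Unreliable TOF readings | Kept in intention-to-treat; excluded in a sensitivity analysis |

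Items 2 and 3 are conditional, because those events may prevent a pain score. Item 6 is categorical, although its event does not prevent one. If uncertain depth of block were the reason, it would apply to IAP as much as to pain, and item 10 patients would be treated alike. Monitor failure is also absent from the list of removal criteria that opens Section 13.0.

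**2. IAP.** Item 6 cuts the series at the failure. Section 14.0 analyses all recorded IAP and names one cut-off, which is not this one. Section 4.1 leaves it unclear whether later readings would be collected.

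**3. Definition.** Item 6 presupposes data before the failure, whereas item 10 says these patients have no TOF readings. If the device never obtains a baseline, the failure comes during induction, before insufflation. Data up to that point then hold no IAP reading, so the patient cannot meet the one-reading rule for IAP, although item 6 calls the patient evaluable for IAP.

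**4. Size.** Inputs from Section 14.0: pain 1.3 against 0.975 on the log scale, SD 0.5, type I error 0.025 per endpoint, 1:1 allocation, 130 randomised, 120 evaluable. Sidedness is not stated, so two-sided is assumed.

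- Standardised difference: d = (1.3 − 0.975)/0.5 = 0.65.
- Power comes from the noncentral t distribution with n1 + n2 − 2 degrees of freedom and noncentrality d/√(1/n1 + 1/n2).
- Reproducing the plan: 60 per arm gives noncentrality 0.65/√(2/60) = 3.56 and power 90.0%. The planned 120 therefore corresponds to 90% power for pain alone.
- Fewer than 10 events means at most 9: 9/130 = 6.9%, leaving 130 − 9 = 121.

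| Lost from pain analysis | Analysed (arms) | Pain power |
|---|---|---|
| 0 | 130 (65/65) | 92.3% |
| 1 | 129 (64/65) | 92.1% |
| 3 | 127 (63/64) | 91.7% |
| 9 | 121 (60/61) | 90.2% |

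The number of monitor failures is not given. The last row takes every anticipated event to be a monitor failure, which is the extreme case within the plan's expectation.

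**The case against.** The strongest reply is that item 6 is itself the exception. It stands in the same section as the general rule, a specific rule can qualify a general one, and Section 4.1 points the same way by taking the patient off protocol. Section 14.0 also refers to the Section 13.0 scenarios when it explains why 130 are randomised to obtain 120. This stands in part: a reader might infer that the plan states no exception and contradicts itself outright, and that goes too far. What remains is that the evaluability sentence in Section 14.0 does not carry the exception, no reason is given for dropping pain alone, and neighbouring items treat comparable patients differently.

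The IAP half is open to more doubt. The sentence about all recorded IAP is followed by one on crossover, so it may be mainly about the arm of analysis. Section 14.0 already truncates once, and items 2 to 4 also use data up to the event, although there the event itself largely ends data capture. Since later readings may not exist, this stays a secondary point.

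The wording on absent TOF readings may simply be loose. It still needs aligning, because it decides who belongs to item 6.

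Finally, power is defined in Section 14.0 as success on at least one endpoint. On that definition, with the plan's assumption of independence, power is at least 99.3% even if nine patients came off 120 rather than 130. The case for a change therefore cannot rest on power.

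**Conclusion.** The point holds as a matter of analysis-set definition, mainly for pain. Applied as written, item 6 removes observed pain scores that the general rule keeps, for a reason unrelated to whether pain was measured. The conflicts over IAP after the failure and over who counts as an item 6 patient are real but secondary.

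The consequence is small: at most 9 of 130 patients, with pain power no lower than 90.2%. This rests on the plan's design values, a two-sided test, and the plan's expectation of fewer than 10 events in all.

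A reader might go further and infer that the exclusion biases the pain comparison. The documents do not support that, because nothing in them links monitor failure to the allocated arm. Nor do they support a claim that the trial becomes underpowered. The change is worth making because it is cheap and settles the primary analysis sets before the data are analysed.

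**What to change.** - **Section 13.0, item 6:** state that patients with TOF monitor failure are evaluable for each primary endpoint for which they have at least one recording, and that all their recorded NPS and IAP values are analysed in the randomised arm. IAP stays subject to the existing Section 14.0 rule on unblinding beyond 15.
- **Section 4.1:** state that coming off protocol for this reason ends neither outcome collection, including the hour 6 research assessment form, nor analysis in the randomised arm.
- **Section 13.0, item 10:** describe item 6 patients as those whose TOF readings are absent or stop because the device failed. Keep this distinct from the item 10 subgroup with bedside readings but no data available for correction.
- **Section 14.0:** add item 6 patients to the exclusions in the sensitivity analysis already planned for monitoring issues.

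If the exclusion is intended, a cross-reference in Section 14.0 and a stated reason would remove the ambiguity, but observed pain scores would still be discarded.

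The cost is protocol wording, one more exclusion in an existing sensitivity analysis, and an hour 6 form for a few patients. The downside is slight dilution of the primary comparison by patients with uncertain depth of block, which the extended sensitivity analysis would help to show.
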